Suicide risk is managed by peer mentors via a structured protocol (Other Attachment IIA, page 39-40). At each session, peers ask participants if they are thinking about suicide or have made a recent suicide attempt. If endorsed, additional questions regarding plans and intent are asked. Depending on the participant's responses, the peer mentor will immediately contact a study clinical supervisor (psychiatrist or clinical psychologist) who may speak with the participant to determine the appropriate disposition (e.g., activate emergency medical services) or provide further instructions. The participant's mental health clinician(s) will also be notified of an increase in suicide risk. This protocol was successfully used during the R34 pilot study, and in two instances participants were referred to emergency medical services based on acute risk.

Overall Compliance

A participant will be done with the intervention when they have completed the last session with the peer mentor, which will typically occur within one week of the 3-month outcome assessment.

Treatment Design

During the intervention development phase of the R34 project, an expert panel including suicide prevention researchers ([name], [name], [name]), peer support researchers ([name], [name]), peer specialists ([name], [name]), the peer support training director for the State of Michigan ([name]), and an inpatient psychiatry unit director ([name]) were convened to create an outline of the essential training needs for peer mentors to work with high-risk patients and address suicide risk according to the interpersonal theory of suicide. The outline of the training and intervention content was then used as the basis for developing the training manual (Other Attachment IIA). This manual was developed by the PI ([name]) in conjunction with [name] and [name] of the Center for Dignity, Recovery, and Empowerment (a peer support advocacy, service, and research organization); [name], a clinical psychologist with expertise in peer support; and [name], a clinical psychologist and post-doctoral fellow. Drafts of the training materials were circulated among the expert panel and revised in an iterative process.

Interventionist Training

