The peer mentor selected by the participant will then meet with the participant the next day while the participant is still in the hospital. This first session is intended to break the ice, establish "peerness" by the peer mentor briefly sharing some of his or her personal experience with mental health challenges and/or suicidal thinking or behaviors, and discuss how future sessions will proceed and the limits of confidentiality, particularly in the case of acute suicide risk.

Subsequent sessions will be scheduled according to the participant's preferences, with a suggested maximum frequency of twice weekly for the first two weeks, weekly for weeks 3 to 8, and then every other week for the last month. In the R34 trial, participants' preferences and availability for contact varied widely, though several participants who completed only a few mentorship sessions still expressed appreciation of the visits during semi-structured qualitative assessments at 3 months. Allowable meeting locations include public places in the community (e.g., coffee shop, park), the participant's home, or a research clinic space. Meetings can also be by phone, which comprised 26% of sessions in the R34.

Preference for the 3-month timeframe was assessed and confirmed by peer mentors and participants during the R34. In order to minimize possible distress that participants may experience at the loss of support at 3 months, and to protect participants to whom an abrupt end to the peer relationship may be harmful, peer mentors may offer participants the option of 3 additional sessions over 4 weeks following the end of the 3-month intervention. These additional sessions will take place over the phone.

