Though these adverse events are considered expected for the study population; determining that an event is “unrelated” to study activities requires comprehensive evaluation and tracking for the population of this study. In order to ensure patient safety and monitor any disparity between the intervention and enhanced usual care groups, a study specific reporting plan will be used for the two most serious expected adverse event categories. Suicide deaths and medically serious suicide attempts will be reported to the IRB as “unlikely related” at minimum, as potential changes in trajectory due to study participation should be monitored for both intervention groups. A brief records review will be completed for suicides and hospitalizations in order to confirm that there is no mention of study participation as a causal factor. Please see below for reporting timetable and guideline detail. These events will be reported to the DSMB bi-annually, unless frequency increases beyond that which is expected for the population. Of note: If there is evidence that an adverse event is “related” to study participation, it will be reported individually within 14 calendar days of study team discovery per standard reporting guidelines.

Reporting Plan

Note: Adverse events **not** listed above will be reported using the standard reporting guidelines and timetable

Event	Relation to study	Reporting Timeframe
Suicide death	Reported as “unlikely related” at minimum.	Individually within 7 days of study team discovery.
Medically serious suicide attempt	Reported as “unlikely related” at minimum.	Individually within 7 days of study team discovery.
Psychiatric hospitalizations or emergency room visits due to suicidal intent or behavior	Unrelated	Not reported per standard reporting guidelines.
	Related	Reported individually within 14 calendar days of study team discovery per standard reporting guidelines.
Suicide attempts not requiring medical hospitalization	Unrelated	Not reported per standard reporting guidelines.
	Related	Reported individually within 14 calendar days of study team discovery per standard reporting guidelines.
Breach of confidentiality associated with reporting suicidality to agency staff, appropriate authorities, and/or mental health personnel.	Unrelated or Related	Not reported per standard reporting guidelines.
Suicidal thought	Unrelated or Related	Not reported per standard reporting guidelines.

Safety Monitoring

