[name] in cooperation with Co-Investigators will be responsible for providing training to all research staff working with participants with regard to procedures for managing potential clinical deterioration, suicidal crisis situations, and/or adverse events. This training will include information regarding evaluating warning signs of acute suicidal ideation, planning, or intent that could occur during contact with participants, and means of addressing such issues. Peer mentors will inquire about suicidal ideation at every encounter with participants, and participants complete self-report measures of suicidal ideation at baseline, 3-month, and 6-month assessments conducted by RAs. In the case that a participant indicates any level of suicidal ideation or recent attempt during encounters with any study staff (including peer mentors), a suicide risk management protocol will be used. The protocol utilizes an algorithm of scripted risk assessment questions and “action steps” dependent on the participant responses. Based on the level of risk determined by the algorithm, study staff may perform one or more of the following: a) recommend the participant call or be transferred to the national suicide crisis hotline, the University of Michigan’s Psychiatric Emergency Services (PES), or the nearest emergency department to immediately address suicide risk and determine whether emergency medical services or police should be activated to conduct a wellness check in the patient’s home or community, b) notify the participant’s outpatient treatment providers regarding a non-imminent increase in suicide risk, c) notify a designated on-call study team clinician ([name], [name], or [name],) when the suicide risk management algorithm has been activated, and when any questions arise regarding risk management. The on-call study clinician will be available via pager or cell phone at all times when there is potential contact between study staff (including peer mentors) and participants.

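### Only the PREVAIL arm is asked about recent attempts at every mentor session, so by-arm counts of medically serious attempts are open to detection bias toward apparent harm

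*Combined protocol and SAP*

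**What the plan says.** **Enquiry in one arm only.** Treatment Fidelity states: "At each session, peers ask participants if they are thinking about suicide or have made a recent suicide attempt". Depending on the answers, the mentor contacts a clinical supervisor at once. Weekly supervision also reviews every active participant. Delivery of Treatment gives the suggested maximum session frequency as "twice weekly for the first two weeks, weekly for weeks 3 to 8, and then every other week for the last month", after a first meeting in hospital. Up to 3 telephone sessions may follow in the 4 weeks after the 3-month intervention.

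**Enquiry in both arms.** Enhanced usual care (EUC) is one caring message 24 to 72 hours after discharge, and PREVAIL participants receive it too. Retention describes a contact 48 hours after discharge to re-introduce the study. Blinded staff assess both arms at 3 and 6 months. Under Secondary Outcomes, medical records are sought when a participant reports relevant care at one of those assessments.

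**Use of the counts.** The Event Reporting Schedule says that, to "monitor any disparity between the intervention and enhanced usual care groups, a study specific reporting plan will be used" for the two most serious expected categories: "Suicide deaths and medically serious suicide attempts will be reported to the IRB". The timeframe is "Individually within 7 days of study team discovery". On the DSMB it says: "These events will be reported to the DSMB bi-annually, unless frequency increases beyond that which is expected for the population". Monitoring adds that the DSMB is told promptly of all serious adverse events and advises on continuation. Hospitalization is part of the serious adverse event definition.

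The text I could read does not ask for the source of discovery to be recorded, and does not caution that detection differs between arms.

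**The concern.** A comparison of event counts between arms is informative only if events have a similar chance of becoming known in each. Here the count starts from discovery by the study team, and one arm has an extra route to discovery that the other lacks. Extra questioning can add known events or bring them forward; it cannot remove any. The distortion therefore runs one way, toward more known events in PREVAIL. A difference could reflect detection alone, or a real benefit could look smaller than it is. The DSMB would have no means of separating these from the counts.

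Mentor escalation can add to this. In the pilot, two participants were referred to emergency services through the mentor protocol. Where such a referral leads to admission, it is a hospitalization event with a source that exists only in PREVAIL.

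**Working it through.** The plan gives no figure for unequal detection, so none can be reproduced. The steps below set the routes side by side and then show what the bias could look like under stated assumptions.

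**1. Contacts.** The suggested maximum after discharge is 2 × 2 (weeks 1–2) + 6 (weeks 3–8) + 2 (last month) = 12 sessions, plus the hospital meeting and up to 3 optional calls. The pilot mean was 5.6 encounters over 3 months (SD 4.8), which may include the hospital meeting. Each arm has 2 scheduled assessments. These numbers show that the asymmetry is real. They do not measure bias, because repeated questions about the same period do not multiply events.

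**2. Which counts are exposed.**

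| Count | Found by mentor questioning? | Common route |
|---|---|---|
| Suicide death | Hardly | Not dependent on interview |
| Medically serious attempt | Yes | 3- and 6-month C-SSRS, Health Services Inventory, and records they trigger |
| Hospitalization reported as a serious adverse event | Yes, and can follow a mentor referral | Health Services Inventory at 3 and 6 months |
| Primary C-SSRS outcome | No | Blinded assessments in both arms |

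**3. Missed assessments.** Assume equal true rates, every attempt known among assessed participants, and an attempt missed at the assessment not recovered later. Let f be the share assessed and m the share of attempts among unassessed participants that mentors detect. Then

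ratio of known attempts, PREVAIL:EUC = [f + (1 − f)m] / f = 1 + m(1 − f)/f.

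Inputs for f are 0.79 (pilot 3-month follow-up, 49 of 62) and 0.75 (the 25% dropout in Sample Size; 490 × 0.75 = 367.5, the plan's 368). The documents give no value for m; 0.25 to 1 is assumed.

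- f = 0.79: (1 − f)/f = 0.266, so the ratio is 1.07 at m = 0.25 and 1.27 at m = 1.
- f = 0.75: (1 − f)/f = 0.333, so the ratio is 1.08 at m = 0.25 and 1.33 at m = 1.

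The base rate cancels. That matters because the pilot's 24% at 3 months is for any attempt, and the documents give no rate for medically serious ones. The low end is more plausible if people who miss assessments also leave mentoring; with m = 0 the ratio is 1.

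**4. Timing.** Assume even accrual of 490 over 3 years: 490/36 = 13.6 per month. At a review 6 months after the first enrollment, about 82 are enrolled (13.6 × 6), and about 41 (13.6 × 3) have not reached 3 months. For those 41 no scheduled common enquiry has taken place, while mentors have been asking the PREVAIL half. The share not yet at 3 months is 3/t for a review at month t of recruitment: 50% at 6 months, 25% at 12 and 8% at 36. This route exists even with perfect follow-up and fades as the trial matures.

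**The case against.** The strongest reply is that the events at issue are those both arms can recover. A medically serious attempt usually means hospital care, and the 3- and 6-month assessments ask about it and trigger record retrieval. Mentoring typically ends within a week of the 3-month visit. For an assessed participant, mentor questioning therefore mostly changes when an event is known, not whether. This stands, and it confines the lasting excess mainly to participants who miss assessments but still see a mentor. It does not answer the interim timing problem.

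Several stronger readings are tempting but unsupported:

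- A reader might infer that safety counts in general are biased. The disparity plan covers only two categories, and deaths are little affected. The Training section's "Peer mentors will inquire about suicidal ideation at every encounter with participants" concerns ideation, which is not reported under that plan.
- A reader might take 5.6 + 2 = 7.6 contacts against 2 as the size of the bias. It counts contacts only.
- A reader might say that the plan pools events from all sources. It does not say so; this is an inference from a discovery trigger with no limit on source.
- A reader might conclude that the DSMB would be misled on stopping. No between-arm safety test or arm-based stopping rule appears, the stated escalation is against the frequency expected for the population, and the DSMB has statistical expertise and sets its own triggers.

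I did not have all of the Monitoring section, nor the Manual of Procedures, event forms or DSMB working documents. The absence of a source field is claimed only for the text I could read.

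**Conclusion.** The point holds as a limited one about safety reporting. Followed as written, the plan produces a by-arm count of medically serious attempts, and of any hospitalizations sent to the DSMB, in which PREVAIL events have an additional way of becoming known. The direction is toward apparent harm. It matters most at early DSMB reviews, before EUC participants reach 3 months, and later among participants who skip assessments but keep seeing a mentor.

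The size cannot be derived from the documents. The 1.07 to 1.33 range is an illustration that rests on the assumed m, on equal true rates and on no later recovery of missed events; the true figure may be smaller. The primary analysis needs no change on this account. This is a cheap improvement that makes a comparison the plan already intends interpretable, not a flaw that threatens the trial's conclusions.

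**What to change.** Record for each event the source of discovery (scheduled assessment, record retrieved because of an assessment, mentor session, spontaneous or other) and the date of discovery. In DSMB reports and the final safety tables, show by-arm counts twice: from all sources, and from the sources common to both arms, meaning the 3- and 6-month assessments and the records they trigger. Identify mentor-detected events, and add a note that ascertainment differs between arms. If data collection has ended, the source may be recoverable from existing notes.

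Keep the all-source counts. Leave all individual reporting timelines and safety responses as they are.

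The cost is a small addition to the event form and one extra table. There is one real drawback: common-source counts lag behind and can miss true events, permanently so for participants lost to follow-up. Replacing the all-source counts with them could delay or hide a real harm signal, so both must be shown.

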The primary outcome is to determine the effectiveness of the PREVAIL peer mentorship intervention for reducing suicide attempts and suicidal ideation among recently hospitalized adult psychiatric patients at high risk for suicide. In a two-site, randomized controlled trial (N=490), participants in the 3-month peer mentorship intervention arm will be less likely to report a suicide attempt on the Columbia Suicide Severity Rating Scale (CSSR-S) and will report less severe suicidal ideation on the Beck Scale for Suicidal Ideation (BSI) over the 6 months following enrollment compared to those in an enhanced usual care control condition.

1. Suicide attempts (measured by the Columbia Suicide Severity Rating Scale) [Time Frame: 6-months]
Any suicide attempt as measured according to an electronic self-report version of the Columbia Suicide Severity Rating Scale (CSSR-S). The definition of suicide attempt for the primary outcome will consist of any actual suicide attempt, aborted suicide attempt, or interrupted suicide attempt according to the CSSR-S.
2. Change in suicidal ideation (measured by the Beck Suicide Scale (BSS)) [Time Frame: Baseline, 6-months]
Patient's current suicidal ideation as measured by the Beck Suicide Scale (BSS). The BSS is a self-report 19-item scale preceded by five screening items. The BSS and its screening items assess thoughts, plans and intent to commit suicide. All 24 items are rated on a three-point scale (0 to 2). Total scores could range from 0 to 48 (if the screening items are included). No specific cut-off scores exist to classify severity. Increasing scores reflect greater suicide risk.

Secondary Outcomes

1. Medically serious suicide attempts (measured by the medical record) [Time Frame: 6-months]
Any suicide attempt as notated in the patients electronic medical record. The definition of suicide attempt for the primary outcome will consist of any actual suicide attempt, aborted suicide attempt, or interrupted suicide attempt.

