We will examine the randomization process to determine if there were any between-group differences at baseline, particularly in variables that are thought to be potentially associated with suicide attempts or ideation. T-tests or chi-square analyses, as appropriate, will be used to test for differences in the following baseline variables between study groups: age, severity of suicidal ideation prior to admission, burdensomeness, hope/hopelessness, and measures of belongingness. When there are significant differences in the distribution of these variables, they will be included as covariates in multivariable analyses. Balance is expected for sex and recent suicide attempt due to randomization by minimization.

Data Verification/Univariate Analyses: We will examine the distribution of all study variables for extreme values, missing data, variances, possible coding errors, skewness and whether or how to categorize skewed data. We will describe means (SD) for the continuous measures and frequencies of dichotomous outcomes by study group for each assessment time for the entire sample and for each of the study sites, separately.

Primary Outcome

Primary analyses will determine the effectiveness of PREVAIL in decreasing the risk of any suicide attempt and in decreasing suicidal ideation at 6 months post-randomization. Primary analytic cohort will be "intent to treat", such that all randomized participants will be included according to their original study arm assignment, regardless of whether they subsequently drop out of participation in the intervention. Secondary analyses will be conducted using a "per protocol" cohort where only participants who complete 6 or more peer encounters will be compared to those assigned to the EUC arm. We will evaluate predictors of compliance by defining 6 or more peer encounters as compliance and will also obtain complier average difference (a.k.a. complier average causal effect) assuming a balanced proportion of compliance between arms. The estimates of the three analytic cohorts (intent to treat, per protocol and compliance average difference) will provide more robust understanding of the effect of PREVAIL. (106)

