Bivariate/Multivariate Analyses: To test for intervention effects at 6 months on the primary outcomes, a logistic regression model will be used for the dichotomous outcome of suicide attempt (as assessed by CSSR-S) and a multiple regression model will be used for suicidal ideation (as assessed by BSI). Each model will include the study arm as the primary predictor and will also include study site, gender, and prior suicide attempt, which were the balancing variables used in randomization. We will also adjust for additional covariates that show imbalances in baseline analyses. Outcomes at 6

[figure not shown]
months post-randomization will be our primary analysis in order to assess whether the intervention has lasting effects, but we will also assess immediate effects at 3 months using similar analytic approaches.

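### The secondary per-protocol contrast selects only the PREVAIL arm on attendance after randomization, so it can show an effect in either direction when there is none, yet the SAP presents it without a caveat

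*Combined protocol and SAP*

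**What the plan says.** The SAP, under Primary Outcome, makes ITT the primary analysis. It then adds two adherence analyses at the same threshold of 6 encounters.

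- A secondary per-protocol cohort, in which "only participants who complete 6 or more peer encounters will be compared to those assigned to the EUC arm".
- A complier average difference ("complier average causal effect) assuming a balanced proportion of compliance between arms").

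It also says "We will evaluate predictors of compliance by defining 6 or more peer encounters as compliance", and that the ITT, per-protocol and complier estimates together "will provide more robust understanding of the effect of PREVAIL". It gives no caveat on the per-protocol estimate and no rule for reading it if it disagrees with the ITT.

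Under Bivariate/Multivariate Analyses, "Each model will include the study arm as the primary predictor and will also include study site, gender, and prior suicide attempt", plus baseline variables found to be imbalanced. The text does not say whether this adjustment applies to the per-protocol cohort, or whether the predictors of compliance enter that model.

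Four other places bear on the point:

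- **Delivery of Treatment:** sessions follow the participant's "preferences, with a suggested maximum frequency of twice weekly for the first two weeks, weekly for weeks 3 to 8", then every other week. In the pilot, "preferences and availability for contact varied widely".
- **Primary Outcomes:** attempts and ideation are assessed "over the 6 months following enrollment compared to those in an enhanced usual care control condition".
- **Preliminary Studies, Acceptability and feasibility:** the pilot mean was 5.6 encounters (SD 4.8) over 3 months, against a target mean of 4. The commonest reason for having no encounter after discharge (n=9) was being overwhelmed or short of time.
- **Preliminary Studies, Outcomes and safety:** 24% of pilot participants reported an attempt by 3 months.

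**The concern.** EUC participants have no encounters, so the threshold can act on only one arm. What remains is a self-selected part of PREVAIL set against all of EUC, and randomization no longer protects the comparison. Two routes lead to bias.

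1. **The outcome drives attendance.** Attempts count from enrollment, while encounters are still accruing. A PREVAIL participant who attempts before the 6th encounter and then stops leaves the cohort, whereas the EUC counterpart stays in. This favours PREVAIL.
2. **Prognosis drives attendance.** If lower-risk people attend more, the contrast favours PREVAIL. If more distressed people seek more sessions, it goes against PREVAIL.

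Baseline covariates, even if applied here, remove only the part of the second route that they explain. They cannot remove selection caused by an attempt after baseline.

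What is at stake is interpretation. A per-protocol benefit beside a null ITT could be taken as support for PREVAIL among those who engage, or a real benefit could be understated.

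**Working it through.** **The plan's own figure.** The SAP gives no figure for the per-protocol contrast. Its 84% power is for the primary comparison (22% vs 36%, 184 per group, two-sided 0.05) and reproduces. The standard error (SE) under the null is sqrt(2 × 0.29 × 0.71 / 184) = 0.0473, and under the alternative sqrt((0.36 × 0.64 + 0.22 × 0.78) / 184) = 0.0467. Then (0.14 − 1.96 × 0.0473) / 0.0467 = 1.01, giving 84.4%. That figure is not in dispute.

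**Inputs for the illustration**

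- True null with 29% attempts by 6 months in both arms, the midpoint of 22% and 36%.
- Share reaching 6 encounters: about 41% if pilot counts (mean 5.6, SD 4.8) are negative binomial, about 51% if normal. Both distributions are assumed.
- Timing of the 6th encounter at the suggested maximum: two sessions a week for two weeks gives 4, then weekly. The 6th falls in week 3 if the inpatient meeting counts and in week 4 if not.
- Attempt timing (assumed): even over 26 weeks, or front-loaded to 24% by 13 weeks.
- Stopping rates and risk ratios are assumed; the documents give none.

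**Route 1: stopping after an early attempt.** Let q be the probability of an attempt before the 6th encounter and s the share of those who then stop. Attendance is otherwise unrelated to risk.

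Spurious benefit = 0.29 − (0.29 − sq)/(1 − sq) = 0.71·sq/(1 − sq)

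| Timing | q | s = 25% | s = 50% |
|---|---|---|---|
| Even, week 3 | 0.29 × 3/26 = 0.0335 | 0.6 points | 1.2 points |
| Even, week 4 | 0.29 × 4/26 = 0.0446 | 0.8 | 1.6 |
| Front-loaded, week 3 | 0.24 × 3/13 = 0.0554 | 1.0 | 2.0 |
| Front-loaded, week 4 | 0.24 × 4/13 = 0.0738 | 1.3 | 2.7 |

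In these eight cells, simulation with 184 EUC against about 75 PREVAIL participants puts the chance of a falsely significant benefit at about 3-6%, against a nominal 2.5%.

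The second case has fewer sessions that follow the same taper. It was simulated with negative binomial attendance and places the 6th encounter at about week 6.6. The spurious benefit at s = 25% and 50% is 1.3 and 2.7 points with even timing, and 2.3 and 4.7 front-loaded. At s = 0 the bias is zero.

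**Route 2: a prognostic link.** Let c = 0.41 reach 6, with RR times the risk of those who do not. Then p0 = 0.29/(c·RR + 1 − c) and p1 = RR·p0.

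- RR 0.8: p0 = 0.29/0.918 = 0.316, p1 = 0.253. Difference 3.7 points in favour of PREVAIL.
- RR 1.25: p0 = 0.29/1.1025 = 0.263, p1 = 0.329. Difference 3.9 points against PREVAIL.

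**Scope.** These figures are for attempts. For ideation, measured as a current state at 6 months, only the second route carries over directly.

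**CACE under the same conditions.** The instrumental estimate is the ITT difference divided by c. With outcomes fully observed, a null ITT gives a null CACE whatever the link between attendance and risk. It has two costs.

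- **Precision:** its SE is 0.0473/0.41 = 0.115, against sqrt(0.29 × 0.71 × (1/184 + 1/75)) = 0.062 for the naive contrast. The ratio is about 1.9, or about ±22.6 points against ±12.2.
- **Exclusion restriction:** it credits the whole ITT difference to those reaching 6. At the planned 14-point difference it would read 14/0.41 = 34.1 points. That is too large if fewer sessions also help.

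**The case against.** The plan handles much of this already. ITT is primary, the per-protocol contrast is labelled secondary, predictors of compliance will be examined, and a CACE at the same threshold is planned. No passage makes an effectiveness claim depend on the per-protocol result. All of that stands, and it limits the point to wording: a missing caveat and a missing reading rule.

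The magnitudes are also assumed throughout. At the maximum schedule with 25-50% stopping they are modest, and they may be zero. That stands too. What the objection does not answer is that the text offers this contrast as adding robustness, when it can disagree with the ITT for reasons unrelated to any effect.

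The CACE at 6 is itself open to challenge. Its assumption that fewer than 6 encounters does nothing sits badly with a pilot target mean of 4 and pilot participants who valued only a few sessions. This stands and shapes the fix.

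A reader might infer three stronger things that the documents do not support:

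- **That the bias must favour PREVAIL.** The pilot reason for non-attendance leans towards a prognostic link, but it covers nine people and mixes distress with lack of time. Preference-led sessions allow the opposite direction.
- **That the bias is large.** Figures of 7 points (even timing) to 12.5 (front-loaded) arise only if every early attempter stops and sessions are equally spaced over 12 weeks. The protocol suggests a tapering schedule and gives no stopping rate.
- **That the CACE at 6 is a clean replacement.** It depends on the exclusion restriction and on how the assumed 25% dropout is handled.

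**Conclusion.** The concern holds for a secondary analysis; the primary inference is untouched. As written, the per-protocol contrast is not a randomized comparison and can show a difference in either direction under no effect. Neither the planned covariates nor the unlinked predictors of compliance can be relied on to remove this.

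Plausible sizes for attempts are from under 1 to about 5 points of spurious benefit if 25-50% of early attempters stop, or nearly 4 points either way under a modest prognostic link. These rest on a 29% null, assumed attempt timing and stopping rates and, beyond the maximum-schedule cases, an assumed attendance distribution. They show what could happen and do not estimate the bias in this trial. The change is worth making because it is cheap and governs what may be concluded from discordant results.

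**What to change.** In the SAP, Primary Outcome:

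1. Label the one-arm per-protocol contrast as descriptive and subject to selection bias in either direction, or drop it.
2. Take it out of the set of estimates said to strengthen understanding of the effect. State that if it differs from the ITT, it is not evidence of effectiveness.
3. Keep the planned CACE as the adherence analysis, with randomization as the instrument. Name the estimator, and state that it assumes fewer than 6 encounters has no effect.
4. Because that assumption is doubtful here, add a CACE with a lower cut-off, for example any encounter, as a sensitivity analysis. State that the CACE at 6 probably overstates the complier effect if fewer sessions also help.
5. Say whether the inpatient meeting and the optional extra sessions after 3 months count as encounters. This matters especially for a cut-off of any encounter, since 95% of pilot intervention participants had the inpatient meeting; if it counts, that estimate will lie close to the ITT.
6. Say how missing outcomes are handled in the CACE, given the assumed 25% dropout.

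The cost is SAP wording and one further run on encounter counts already needed. The price in precision is a CACE interval about 1.9 times as wide as the naive per-protocol one at 41% reaching 6. The narrower interval takes no account of the selection.
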